**Procedures.** We will enroll participants with IBD (n=56 total) in a biofeedback enhanced cognitive behaviorally based coping skills treatment. Participants will be randomized to biofeedback enhanced treatment (n=28 for IBD) or wait-list control (n=28 for IBD). Autonomic reactivity in response to stress induction and coping strategies will be measured at time of random assignment, at treatment end, and at 2-months follow-up to compare to wait-list control participants completing assessment only (n=28 for IBD). Treatment will consist of a 6-visit group intervention conducted online, via Emory zoom. Groups will include 5-8 patients. Groups will meet approximately each week for 6 weeks. I will train advanced PhD students in clinical psychology to assist me in delivering the treatment protocol. Trained research assistants who are not delivering the treatment will conduct all assessments. Sessions will include brief, daily homework to facilitate mastery that is developmentally tailored to youth (e.g., practice skills with support from phone or tablet apps). We anticipate that following treatment, participants will demonstrate statistically significant decreases in autonomic reactivity compared to wait-list control participants. Wait-list Control: Participants randomized to the wait-list control group will complete the same measures of lifetime stress, autonomic reactivity, depression, anxiety. The identical treatment will be offered to control participants after the 6-week time point.

Content of treatment will include:

Biofeedback Enhanced Coping Skills Treatment Protocol		Treatment Targets			
Session Content		Coping with illness	Anxiety Symptoms	Depressive Symptoms	Autonomic Dysfunction
1	Disease education; Goal Setting	X			
2	Deep breathing; Guided imagery; Progressive muscle relaxation	X	X		X
3	Biofeedback		X	X	X
4	Mindfulness-based exposure to negative emotions; Biofeedback		X	X	X
5	Pleasant activity scheduling; Biofeedback practice	X		X	
6	Biofeedback Maintenance Plan		X	X	X

6. Study design and methods:

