**Intervention:** As a follow-up to our observational studies described above, we have developed a biofeedback enhanced cognitive behavioral therapy to address symptoms of psychophysiological reactivity and anxiety and depression. We plan to enroll up to 56 patients with IBD in this intervention. Participants will be randomized to biofeedback enhanced treatment (n=28 patients with IBD) or wait-list control (n=28 patients with IBD). Autonomic reactivity in response to stress induction, symptoms of anxiety and depression, and coping strategies will be measured at time of random assignment, at treatment end, and at 2-months follow-up to compare to wait-list control participants completing assessment only (n=28 patients with IBD). Patients will also rate their disease symptoms and measures of clinical disease activity will be collected via chart review.

Potential participants will be recruited based on patients with IBD for psychological intervention and advertising through patient email listserves.

Treatment will consist of a 6-visit group intervention conducted via Emory zoom. Groups will include 5-8 patients each. I will train advanced PhD students in clinical psychology to assist me in delivering the treatment protocol. Trained research assistants who are not delivering the treatment will conduct all assessments. Sessions will include brief, daily homework to facilitate mastery that is developmentally tailored to youth (e.g., practice skills with support from phone or tablet apps). We anticipate that following treatment, participants will demonstrate statistically significant decreases in autonomic reactivity compared to wait-list control participants. Wait-list Control: Participants randomized to the wait-list control group will complete the same measures of lifetime stress, autonomic reactivity, depression, anxiety. The identical treatment will be offered to control participants after the 6-week time period.

7. If applicable: if data/samples collected for this study will be saved/banked/archived for future use, describe plans, who may use the material, and for what purposes (may require a separate repository-specific IRB submission).

Wave 1 and 2 observational research:

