Wave 1: Participants will be compensated for their time with \$25 gift cards at T1 and \$25 gift cards at T2 and T3 for completion of study questionnaires. Participants will be compensated with an additional \$25 gift card for completion of stool tests within 1 week of study questionnaire completion, to be mailed. Total possible compensation for each subject is \$150 across all 3 time points of the study.

Wave 2: A total of 60 participants (diagnosed with IBD) will be recruited at baseline and receive up to \$60 total for participation in baseline measures. Participants will receive a \$40 gift card after completing patient and parent-report questionnaires and an additional \$20 gift card for providing stool, blood, and DNA samples. The 60 diagnosed with IBD will be enrolled in the longitudinal assessment component of the research plan with 5 subsequent visits at \$45 compensation for each subsequent participation. Participants will receive a \$25 gift card after completing patient and parent-report questionnaires and an additional \$20 gift card for providing stool, blood, and DNA samples. Total possible compensation for each subject with IBD is \$285 across baseline and 5 subsequent assessment points.

Intervention: Participating patients will receive a \$50 gift card for enrolling in the biofeedback enhanced coping skills group treatment. Each participant will earn an additional \$15 in gift cards for attending each of the 6 group treatments. Finally, each participant will earn an additional \$30 for completing post-assessment and follow-up measures, for a total possible compensation of \$200.

11. Statistical analysis: Multi-level modeling will be utilized to estimate children's adjustment at follow-up points after controlling for adjustment at T1. The linear (main) effects of disease activity and physiological reactivity on children's adjustment will be examined as will the interaction between physiological reactivity and disease activity. Contextual risk and perception of stress will be explored as additional moderators in the model.

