In the cross-sectional comparison of IBD patients with age-sex-matched controls, measures of psychophysiological and immune functioning and levels of anxiety, depressive, and disease symptoms will be summarized using standard descriptive statistics. Differences between groups (IBD vs. control) will be made using paired t-test or Wilcoxon signed rank tests to account for paired samples. Linear models will be used to examine the relationship between ANS and neuroimmune function with levels of anxiety, depression and disease symptoms. Specifically, models will include the main effect of group, the main effect of predictor (e.g., physiological reactivity or CRP), and the interaction between group and predictor. The interaction serves as the statistical test to determine if the correlation between predictor and outcome (e.g., anxiety, depression, etc.) differs between IBD patients and controls.

Intervention: Primary goals of the intervention are to establish the feasibility and acceptability of a RCT of enhanced biofeedback to improve autonomic reactivity and reduce levels of depression, anxiety and clinical symptoms in pediatric patients with IBD. Feasibility measures including consent rates, completion/retention rates, and treatment satisfaction ratings will be summarized using counts and percentages or means and standard deviations, as appropriate. Changes in clinical scores (anxiety, depression, and clinical symptoms) and autonomic reactivity from baseline, to end of treatment, and 2 months post treatment will be summarized within groups at each study time-point. The changes in the measures *within* and *across* groups will be analyzed using a two-factor repeated measures analysis of variance model

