(rmANOVA). Models will include the main effect of group, the effect of time and the group X time interaction term. Other baseline covariates including age, disease severity, and other clinical characteristics may be included in the models. Data will be modeled using the *MIXED* procedure in SAS which allows for use of all outcome data, even in the presence of missing data. Differences in group means will be calculated and presented along with 95% confidence intervals. Effect sizes will also be calculated to further describe the degree of difference between groups. Appropriate modeling assumptions will be verified prior to analysis and analysis will follow the intention to treat principal. In exploratory analyses, we will determine whether reductions in anxiety, depression and stress are mediated by changes in autonomic reactivity and coping strategies by exploring the direct and indirect effects of autonomic reactivity and coping strategies on perceived stress, anxiety and depression. For each outcome of interest (e.g., depression), an estimation of the mediation effect will be calculated using the difference in the regression coefficients ( $\beta_1 - \beta_2$ ) obtained from the two linear regression models with and without the mediator (i.e., skin conduction measure or HRV). Bootstrapping (5000 samples) will be used to obtain the empirical distribution of the mediation effect and test the null hypothesis that the difference-in-coefficients ( $\beta_1 - \beta_2$ ) is zero. This method has superior statistical power for relatively small sample sizes and does not require a large effect size.

12. Data and Safety Monitoring and Reporting: The IRB will be notified of any unexpected, adverse events. As this study is low risk, no such events are anticipated. Any adverse events associated with venipuncture will be monitored by the PI and reported to site medical doctors, [name] and patients' primary physician at GI Care for Kids, as well as Emory IRB.

13. Confidentiality:

- Privacy will be protected by handling all in-person conversation and study procedures in private exam rooms.

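### The intervention model names no therapy-group term, so the end-of-treatment 95% CIs are too narrow if outcomes correlate within the groups of 5 to 8

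*Combined protocol and SAP*

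**What the plan says.** Section 5 (Intervention, Procedures) states: "Treatment will consist of a 6-visit group intervention conducted online, via Emory zoom. Groups will include 5-8 patients". Section 6 (Intervention) repeats the size: "Groups will include 5-8 patients each". Each arm has 28 youth at full enrolment.

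Section 6 has outcomes measured at randomization, "at treatment end, and at 2-months follow-up to compare to wait-list control participants completing assessment only (n=28 patients with IBD"). It then says of the wait-list: "The identical treatment will be offered to control participants after the 6-week time period".

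Section 11 describes the intervention analysis as a two-factor repeated-measures ANOVA fitted in SAS PROC MIXED: "Models will include the main effect of group, the effect of time and the group X time interaction term". Patient-level baseline covariates may be added. On reporting: "Differences in group means will be calculated and presented along with 95% confidence intervals". Model assumptions are to be checked before analysis. The same section sets the trial's priorities: "Primary goals of the intervention are to establish the feasibility and acceptability of a RCT of enhanced biofeedback".

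Section 11 opens with a different model ("Multi-level modeling will be utilized to estimate" children's adjustment at follow-up), whose predictors are disease activity and physiological reactivity.

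**The concern.** Youth treated together share sessions, peers and leaders, so their outcomes after treatment may resemble one another. Up to treatment end the wait-list arm has no such structure, so the design is partially nested. A model that treats all 56 youth as independent credits the treated arm with more information than 4 or 5 groups may supply.

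At stake are the error bars and p-values on the between-arm differences in anxiety, depression, clinical symptoms and autonomic reactivity. Sections 5 and 6 expect a statistically significant between-arm difference in autonomic reactivity, so readers will look at these tests. No decision rule is tied to them.

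**Working it through.** **Inputs from the documents.** 28 youth per arm; therapy groups of 5–8; wait-list youth ungrouped up to treatment end. Since 28/8 = 3.5 and 28/5 = 5.6, full enrolment gives 4 or 5 groups. The plan has no power, SD or ICC figure for the intervention, so there is nothing of its own to reproduce.

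**Assumptions.** Post-baseline ICC from 0 to 0.20; within-person correlation r = 0.5, varied from 0.3 to 0.7; equal variance at each visit; clustering only after baseline; complete data. Layouts are 4 groups of 7, and five groups of 6, 6, 6, 5, 5.

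**Step 1: effective group size.** m = (sum of squared group sizes)/28. For 4 groups of 7, m = 196/28 = 7. For the five groups, m = (3×36 + 2×25)/28 = 158/28 = 5.64.

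**Step 2: ICC on the change scale.** With unit variance at each visit, change from baseline has variance 2(1 − r). The group effect enters only after baseline, so change-score ICC = post-baseline ICC / [2(1 − r)]. At r = 0.5 the two are equal. At r = 0.7, a post-baseline ICC of 0.20 becomes 0.20/0.6 = 0.33.

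**Step 3: standard error.** Only one arm is clustered, so true SE / planned SE = √[1 + (m − 1) × change-score ICC / 2]. At ICC 0.10 and r = 0.5 with 4 groups of 7, this is √(1 + 6 × 0.10/2) = √1.30 = 1.140.

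**Step 4: type I error.** Simulated under no treatment effect, using the change contrast with pooled variance, 54 df and 2,000,000 trials per setting, r = 0.5:

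| Post-baseline ICC | SE ratio, 4 groups | SE ratio, 5 groups | Type I, 4 groups | Type I, 5 groups |
|---|---|---|---|---|
| 0 | 1.000 | 1.000 | 5.0% | 5.0% |
| 0.01 | 1.015 | 1.012 | 5.4% | 5.2% |
| 0.05 | 1.072 | 1.056 | 6.8% | 6.4% |
| 0.10 | 1.140 | 1.110 | 8.7% | 7.8% |
| 0.20 | 1.265 | 1.210 | 12.4% | 10.6% |

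CI coverage is 100% minus the type I error: for example, 91.3–92.2% at ICC 0.10. The mean arm difference stayed within 0.0005 of zero throughout, so there is no bias.

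**Step 5: sensitivity to r.** At ICC 0.10, r = 0.3 gives 7.5% (4 groups) and 7.0% (5 groups); r = 0.7 gives 11.1% and 9.7%.

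**Step 6: visit-specific difference.** Section 11 does not say whether its CIs are for change or for the difference at a visit. For the latter, the SE ratio uses the post-baseline ICC directly, so the table applies whatever r is. A separate simulation of that contrast (200,000 trials per setting, adding an 8, 8, 7, 5 layout) gave 6.3–6.9% at ICC 0.05 and 7.8–8.8% at 0.10.

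**The case against.** - *The plan is silent rather than excluding the term.* This is fair. The sentence on model terms lists fixed effects, and no random-effects or covariance structure is written out. PROC MIXED can carry a therapy-group effect, but only if it is specified; Section 11 cites the procedure for its handling of missing data. The promise to verify assumptions names neither therapy group nor a fallback. A data check is also weak with 4 or 5 groups: in simulated change-score fits the group variance was estimated as zero in about 45% of trials at a true ICC of 0.05.
- *Multi-level modeling is already planned.* It is, but for a different question. The intervention has its own paragraph and model.
- *This is a pilot with feasibility goals.* This stands and limits the severity. Section 11 nevertheless commits to between-arm 95% CIs, which should have their stated coverage.
- *The size is assumed.* This also stands. The omission is certain; its effect is not, and at ICC 0.01 it is negligible.

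A reader might infer that the full three-visit arm-by-time test is inflated further. The documents do not support a figure for that, because it would require controls to be untreated at 2 months. Section 6 describes them as assessment-only at that visit but also offers them treatment after 6 weeks.

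**Conclusion.** The point holds conditionally. With any positive within-group correlation after treatment, the end-of-treatment CIs are too narrow and the p-values too small. Under the stated assumptions the inflation is negligible at ICC 0.01, modest at 0.05 and material from about 0.10, and it grows with r.

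A reader might go further and conclude that the estimated effect is biased or that the trial's main conclusions are unsafe. Neither follows: the estimate is unbiased, and the feasibility and acceptability summaries do not use this model. The within-arm change analysis and the bootstrap mediation test do not mention therapy group either; their sensitivity was not quantified. The count of 4 or 5 groups assumes all 28 treated youth enrol, whereas the plan says up to 56 in total.

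This should be corrected before analysis; it is not a fatal flaw.

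**What to change.** 1. Record therapy-group ID for every treated participant, including wait-list youth treated later. Without it, clustering cannot be examined afterwards.
2. Keep the PROC MIXED repeated-measures model, so that participants with a missing visit stay in. Add a therapy-group effect that acts only in the treated arm and only after baseline, with a small-sample df method such as Satterthwaite. A group intercept that is constant over time is not enough, because it cancels from the arm-by-time contrast. This repeated-measures version has not been simulated.
3. Because 4 or 5 groups often give a zero variance estimate, also report the end-of-treatment arm difference with 95% CIs under fixed ICCs. State whether the ICC is on the post-baseline or the change scale, and make the range wide enough: post-baseline 0–0.20 reaches change-score 0.33 at r = 0.7. Stopping at change-score 0.20 in that case leaves a type I error of about 8.1–8.7%.
4. Reconcile the statements on the wait-list arm (assessment-only at 2 months, but offered treatment after 6 weeks) before any 2-month between-arm CI is interpreted. A random effect does not resolve this.

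**Cost.** One variable and a few model lines. Fixed-ICC intervals are about 6–8%, 12–15% and 22–28% wider than planned at change-score ICC 0.05, 0.10 and 0.20. At 0.33 the Step 3 formula gives SE ratios of √(1 + 4.64 × 0.333/2) = 1.33 (five groups) and √(1 + 6 × 0.333/2) = 1.41 (four groups), so they are wider still. These intervals are only as good as the value fixed: fixing 0.20 when the truth is 0 gives a conservative test (1.0–1.4% in simulation), which is why a range should be shown.

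### The intervention's repeated-measures model does not adjust for the baseline value of the outcome, so its treatment contrast is valid but usually less precise than the same data allow

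*Combined protocol and SAP*

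**What the plan says.** The intervention part of section 11 (Statistical analysis) considers clinical scores and autonomic reactivity at three times: "autonomic reactivity from baseline, to end of treatment, and 2 months post treatment will be summarized within groups at each study time-point". Changes within and across groups "will be analyzed using a two-factor repeated measures analysis of variance model", fitted in SAS PROC MIXED so that all observed outcome data are used. The terms are listed: "Models will include the main effect of group, the effect of time and the group X time interaction term". On covariates the plan says only: "Other baseline covariates including age, disease severity, and other clinical characteristics may be included in the models". The baseline value of the outcome is not named, and nothing sets the arms equal at baseline.

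On reporting: "Differences in group means will be calculated and presented along with 95% confidence intervals", with effect sizes in addition. The plan does not say which difference is meant.

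Two other places bear on this. The opening paragraph of section 11, for the observational data, does condition on the starting value: it models "adjustment at follow-up points after controlling for adjustment at T1". The intervention paragraph of section 6 places the first measurement at random assignment and states an expectation: "We anticipate that following treatment, participants will demonstrate statistically significant decreases in autonomic reactivity compared to wait-list control participants".

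**The concern.** When baseline is one of the repeated measurements and each arm has its own free baseline mean, the group-by-time contrast at a later visit subtracts the observed baseline difference in full. Under randomisation the expected baseline difference is zero, so the observed one is chance. Subtracting all of it, rather than the share that predicts follow-up, adds noise unless baseline predicts follow-up one for one.

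The stake is precision, not bias or type I error. With at most 28 per arm the intervals will be wide, and the baseline measurement that could narrow them is already being collected.

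The undefined group difference adds a smaller, conditional risk. If it were taken as the group main effect averaged over all three visits, it would include a pre-treatment visit at which the expected difference is zero.

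**Working it through.** **Inputs from the documents.** 28 + 28 participants; three visits; model terms as listed; 95% intervals. No SD, correlation, effect size or power is stated for the intervention, so there is no figure of the plan to reproduce.

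**Assumed inputs.** Follow-up SD = 1; rho = correlation of baseline with follow-up; k = baseline SD divided by follow-up SD; complete data; independent participants.

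**Step 1: what the planned contrast is.** In a simulated complete data set (56 participants, three visits), the mixed-model group-by-time coefficient at the first post-baseline visit was 0.12162. The difference in mean change was also 0.12162. The identity is exact for complete data. With missing visits the likelihood estimate differs somewhat, but the free baseline difference remains.

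**Step 2: variance at one follow-up visit, relative to follow-up variance.**
- Change score: 1 + k² − 2k·rho
- Baseline-adjusted: 1 − rho²
- Share of variance lost by not adjusting: (k − rho)² / (1 + k² − 2k·rho). At k = 1 this is (1 − rho)/2.

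| k | rho 0.3 | rho 0.5 | rho 0.7 |
|---|---|---|---|
| 1.0 | 35% | 25% | 15% |
| 0.7 | 15% | 5% | 0% |
| 1.2 | 47% | 40% | 33% |

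For example, k = 0.7 and rho = 0.3 give 0.16/1.07 = 15%. At k = 1 the loss runs from 50% at rho 0 to 5% at rho 0.9. The planned standard errors are larger by 1/√0.65, 1/√0.75 and 1/√0.85, that is 24%, 15% and 8%.

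**Step 3: the cost of estimating the baseline slope.** The adjusted variance is multiplied by 1 + 1/(56 − 4) = 1.019. At k = 1 the net variance ratios, adjusted over planned, are 0.65 × 1.019 = 0.66, 0.75 × 1.019 = 0.76 and 0.85 × 1.019 = 0.87. Break-even is rho = 2/1.019 − 1, about 0.96.

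**Step 4: simulation with no true effect.** 20,000 trials per rho at 28 per arm and k = 1 gave ratios of 0.665, 0.763, 0.867 and 0.970 at rho 0.3, 0.5, 0.7 and 0.9. Both estimators were centred on zero (means within 0.003 SD). In 8,000 runs at k = 0.7 and rho = 0.7 the ratio was 1.02, so no gain.

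**Step 5: 95% CI half-width in SD units (k = 1).** Half-width = t × √(2 × variance/28), with the slope cost included for the adjusted version.

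| rho | Planned | Adjusted |
|---|---|---|
| 0.3 | 0.63 | 0.52 |
| 0.5 | 0.54 | 0.47 |
| 0.7 | 0.42 | 0.39 |

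At rho 0.5, 56 participants analysed with adjustment are worth 56/0.764, about 73 analysed by change score.

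**Step 6: the group main effect, if that were reported.** An effect d present at both follow-ups becomes (0 + d + d)/3 = 2d/3. Present only at end of treatment, it becomes (0 + d + 0)/3 = d/3.

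**The case against.** The strongest reply is that nothing here is an error. The planned analysis is standard and unbiased, the primary goals are feasibility and acceptability, and no precision target is set. That stands, and it limits the weight of the point.

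The size of the gain is also uncertain, for three reasons.
- The expectation of statistical significance concerns autonomic reactivity only. Section 4 describes skin conductance reactivity as stable within individuals, so rho may be high for that outcome. At rho 0.8 to 0.9 with equal SDs, the loss before slope cost is only 10% to 5%. Section 4 gives no correlation and says nothing of the kind for heart rate variability.
- Section 8 admits only patients who screen positive for depression or anxiety, which may narrow baseline spread for those scores and push k below 1. As an illustration, start from rho 0.5 and equal SDs, and let selection cut the baseline SD to 0.6 with slope and residual variance unchanged. The loss falls from 25% to 0.09/0.84 = 11%. The screen accepts either of two measures, so the narrowing may be weaker.
- Treatment is given in groups of 5 to 8. Baseline adjustment does not remove therapy-group variance, so the relative gain could be smaller than shown.

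On the text, the optional covariate sentence could be stretched to cover baseline scores. It commits to nothing, however, and adding baseline as a covariate while it also stays among the outcomes would not give the usual adjusted contrast. Nor does the plan say that an all-visit main effect will be reported. If visit-specific group means were intended instead, the loss at each follow-up would be rho² (9%, 25% or 49% at rho 0.3, 0.5 or 0.7), and adjustment would still help. Lastly, the observational model conditions on T1 in a non-randomised setting, so the contrast with it is suggestive rather than an inconsistency.

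**Conclusion.** The concern holds as an efficiency point. The planned group-by-time contrast is valid under randomisation but makes no committed use of baseline as a predictor. With equal SDs and 28 complete, independent participants per arm, a baseline-adjusted contrast has a net 34%, 24% or 13% lower variance at rho 0.3, 0.5 or 0.7. The advantage shrinks to about 3% at rho 0.9 and can disappear when baseline spread is narrow. At this sample size the worst case for adjusting is a variance penalty of about 2%. All these figures rest on assumed rho and k, because the documents give neither. The change is recommended; the pilot's primary goals do not depend on it.

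**What to change.** Keep PROC MIXED and all three visits, use an unstructured covariance, and constrain the two arms to a common baseline mean (a constrained longitudinal model). This retains participants with baseline data only, in line with the plan's aim of using all outcome data and with intention to treat. The alternative is to model the post-baseline visits with the baseline value of the same measure as a covariate, but that drops baseline-only participants.

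Pre-specify the adjusted group difference at end of treatment, with its 95% interval, as the effect estimate, and state that the group main effect averaged over all visits is not the reported difference. End of treatment is the last assessment before the control arm may cross over: "The identical treatment will be offered to control participants after the 6-week time period". Baseline adjustment does not resolve how the 2-month comparison should be read after that offer.

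The cost for the constrained model is SAP wording only: same data, same procedure.
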